11.2.3 Safety Phone Call (Week 0/Day 1)

- Assess AEs.
- Monitor for changes to concomitant medications.
- Remind subjects to complete the BSFS at each occurrence of a bowel movement and the CeD PRO daily.
- Remind subject to complete the weekly GSRS.

11.2.4 Visit 2 (Week 1/Day 7)

- Document visit in the EDC system.
- Collect vital signs.
- Measure body weight.
- Perform physical examination to include an examination of general appearance; HEENT; lymph nodes; respiratory; cardiovascular; gastrointestinal; musculoskeletal; neurological, psychological and dermatological systems.
- Complete PGA BEFORE study drug administration.
- Allow the subject to complete the Patient Global Assessment of Disease (PtGA), BEFORE study drug administration.
- Perform urine pregnancy test on FOCBP.
- Collect blood and urine for clinical laboratory testing.
- Collect blood sample for PK and biomarkers BEFORE start of study drug administration. Record date and actual time of sampling.
- Administer study medication. See section 18 for administration procedures.

NOTE: Subject should remain in the clinic for a minimum of 1 hour after the end of study drug administration to monitor for new AEs.

- Assess AEs.
- Monitor for changes to concomitant medications.
- Remind subjects to complete the BSFS at each occurrence of a bowel movement and the CeD PRO daily.
- Remind subject to complete the weekly GSRS.
- Provide subject with iVYLISA GIP test kit and instructions for home collection.

11.2.5 Visit 3 (Week 2/Day 14)

- Document visit in the EDC system.
- Collect vital signs.
- Measure body weight.
- Perform physical examination to include an examination of general appearance; HEENT; lymph nodes; respiratory; cardiovascular; gastrointestinal; musculoskeletal; neurological, psychological and dermatological systems.

- Complete PGA BEFORE study drug administration.
- Allow the subject to complete the Patient Global Assessment of Disease (PtGA) BEFORE study drug administration.
- Collect blood and urine for clinical laboratory testing.
- Collect blood sample for PK, ADA and biomarkers BEFORE start of study drug administration. Record date and actual time of sampling.
- Collect stool for iVYLISA GIP test. The stool sample will be produced within 3 days prior to, or after, the scheduled study visit.
- Perform urine pregnancy test on FOCBP.
- Administer study medication. See section 18 for administration procedures.

NOTE: Subject should remain in the clinic for a minimum of 1 hour after the end of study drug administration to monitor for new adverse events.

- Assess AEs.
- Monitor for changes to concomitant medications.
- Remind subjects to complete the BSFS at each occurrence of a bowel movement and the CeD PRO daily.
- Remind subject to complete the weekly GSRS.
- Provide subject with iVYLISA GIP test kit and instructions for home collection.

11.2.6 Visit 4 (Week 4/Day 28)

- Document visit the EDC system.
- Allow subject to complete SF-12 v. 2 and EQ-5D.
- Collect vital signs.
- Measure body weight.
- Collect vital signs.
- Complete PGA BEFORE study drug administration.
- Allow the subject to complete the Patient Global Assessment of Disease (PtGA) BEFORE study drug administration.
- Collect blood and urine for clinical laboratory testing.
- Collect blood sample for PK, ADA and biomarkers BEFORE start of study drug administration. Record date and actual time of sampling.
- Collect Whole Blood for Flow Cytometry.
- Collect stool for iVYLISA GIP test. The stool sample will be produced within 3 days prior to, or after, the scheduled study visit.
- Perform urine pregnancy test on FOCBP.
- Administer study medication. See section 18 for administration procedures.

NOTE: Subject should remain in the clinic for a minimum of 1 hour after the end of study drug administration to monitor for new adverse events and to

collect the second PK sample. Collect blood sample for PK 1 hour after END of infusion of study medication.

- Assess AEs.
- Monitor for changes to concomitant medication.
- Dietitian assessment of the GFD. This assessment can be conducted by phone, provided it is conducted within the allotted visit window.
- Remind subjects to complete the BSFS at each occurrence of a bowel movement and the CeD PRO daily.
- Remind subject to complete the weekly GSRS.
- Provide subject with iVYLISA GIP test kit and instructions from home collection.

11.2.7 Visit 5 (Week 6/Day 42)

- Document visit in the EDC system.
- Collect vital signs.
- Measure body weight.
- Perform physical examination to include an examination of general appearance; HEENT; lymph nodes; respiratory; cardiovascular; gastrointestinal; musculoskeletal; neurological, psychological and dermatological systems.
- Perform urine pregnancy test on FOCBP.
- Collect stool for iVYLISA GIP test. The stool sample will be produced within 3 days prior to, or after, the scheduled study visit.
- Administer study medication. See section 18 for administration procedures.

NOTE: Subject should remain in the clinic for a minimum of 1 hour after the end of study drug administration to monitor for new adverse events.

- Assess AEs.
- Monitor for changes to concomitant medications.
- Remind subjects to complete the BSFS at each occurrence of a bowel movement and the CeD PRO daily.
- Remind subject to complete the weekly GSRS.
- Provide subject with iVYLISA GIP test kits and instructions from home collection.

11.2.8 Visit 6 (Week 8/Day 56)

- Document visit in the EDC system.
- Collect vital signs.
- Measure body weight.
- Collect blood sample for PK, ADA and biomarkers BEFORE start of study drug administration. Record date and actual time of sampling.
- Complete PGA BEFORE study drug administration.

- Allow the subject to complete the Patient Global Assessment of Disease (PtGA), BEFORE study drug administration.
- Collect blood and urine for clinical laboratory testing; including sample for biomarkers BEFORE study drug administration.
- Collect Whole Blood for Flow Cytometry.
- Perform urine pregnancy test on FOCBP.
- Collect stool for iVYLISA GIP test. The stool sample will be produced within 3 days prior to, or after, the scheduled study visit.
- Administer study medication. See section 18 for administration procedures.

NOTE: Subject should remain in the clinic for a minimum of 1 hour after the end of study drug administration to monitor for new adverse events. Collect blood sample for PK 1 hour after END of infusion of study medication. Record date and actual time of infusion beginning, end and sampling.

- Assess AEs.
- Monitor for changes to concomitant medications.
- Dietitian assessment of the GFD. This assessment can be conducted by phone, provided it is conducted within the allotted visit window.
- Remind subjects to complete the BSFS at each occurrence of a bowel movement and the CeD PRO daily.
- Remind subject to complete the weekly GSRS.
- Provide subjects with iVYLISA GIP test kit and instructions for home collection.

11.2.9 Visit 7 (Week 10/Day 70)

- Document visit in the EDC system.
- Collect vital signs.
- Measure body weight.
- Collect blood sample for PK and biomarkers BEFORE start of study drug administration. Record date and actual time of sampling.
- Perform urine pregnancy test on FOCBP.
- Collect stool for iVYLISA GIP test. The stool sample will be produced within 3 days prior to, or after, the scheduled visit.
- Administer study medication. See section 18 for administration procedures.

NOTE: Subject should remain in the clinic for a minimum of 1 hour after the end of study drug administration to monitor for new adverse events and to collect the second PK sample.

- Assess AEs.
- Monitor for changes to concomitant medications.
- Remind subjects to complete the BSFS at each occurrence of a bowel movement and the CeD PRO daily.

- Remind subject to complete weekly GSRS.
- Provide subject with iVYLISA GIP test kit and instructions for home collections.

11.2.10 Visit 8 (Week 12/Day 84)

NOTE: DO NOT ADMINISTER STUDY MEDICATION AT THIS VISIT

- Document visit in the EDC system.
- Allow subject to complete SF-12 v. 2 and EQ-5D.
- Collect vital signs.
- Measure body weight.
- Perform physical examination to include an examination of general appearance; HEENT; lymph nodes; respiratory; cardiovascular; gastrointestinal; musculoskeletal; neurological, psychological and dermatological systems.
- Complete PGA BEFORE study drug administration.
- Allow the subject to complete the Patient Global Assessment of Disease (PtGA), BEFORE study drug administration.
- Collect blood and urine for clinical laboratory testing.
- Collect blood sample for PK, ADA and biomarkers. Record date and actual time of sampling.
- Collect Whole Blood for Flow Cytometry.
- Perform serum pregnancy test on FOCBP.
- Collect stool for iVYLISA GIP testing. The stool sample will be produced within 3 days prior to, or after, the scheduled visit.
- Assess AEs.
- Monitor for changes to concomitant medications.
- Dietitian assessment of the GFD. This assessment can be conducted by phone, provided it is conducted within the allotted visit window.
- Remind subjects to complete the BSFS at each occurrence of a bowel movement and the CeD PRO daily.
- Remind subject to complete the weekly GSRS.
- Provide subject with iVYLISA GIP test kit and instructions for home collection.
- Perform endoscopy and collect biopsy specimens within 7 days of Visit 8.

11.3 FINAL STUDY VISIT

11.3.1 Visit 9 (Week 16/Day 112) or 6 Weeks After Last Study Drug Administration

- Document visit in the EDC system.
- Allow subject to complete SF-12 v. 2 and EQ-5D.
- Collect vital signs.
- Measure body weight.

- Complete PGA.
- Allow the subject to complete the Patient Global Assessment of Disease (PtGA) BEFORE study drug administration.
- Perform physical examination to include an examination of general appearance; HEENT; lymph nodes; respiratory; cardiovascular; gastrointestinal; musculoskeletal; neurological, psychological and dermatological systems.
- Collect blood and urine for clinical laboratory testing.
- Collect blood sample for PK, ADA and biomarkers. Record date and actual time of sampling.
- Collect Whole Blood for Flow Cytometry.
- Perform urine pregnancy test on FOCBP.
- Collect stool for iVYLISA GIP testing. The stool sample will be produced within 3 days prior to, or after, the scheduled visit.
- Assess new our ongoing AEs.
- Monitor for changes to concomitant medications.
- Collect eDiary and assure that any outstanding diaries have been entered.

11.4 EARLY TERMINATION (ET)

Early Termination visits should be conducted for randomized subjects (subjects who received double-blind treatment) who discontinue participation in the study. Early termination visit procedures are not required for subjects who do not receive study drug and are therefore considered screen failures.

- Document visit in EDC system.
- Collect vital signs.
- Measure body weight.
- Perform physical examination to include an examination of general appearance; HEENT; lymph nodes; respiratory; cardiovascular; gastrointestinal; musculoskeletal; neurological, psychological and dermatological systems.
- Collect blood and urine for clinical laboratory testing.
- Collect blood sample for PK, ADA and biomarkers. Record date and actual time of sampling.
- Perform serum pregnancy test on FOCBP.
- All attempts should be made to collect a final iVYLISA GIP stool sample, if the sample was not collected within 3 days prior to the scheduled Early Termination visit.
- Assess AEs.
- Monitor for changes to concomitant medications.
- Allow subject to complete SF-12 v. 2 and EQ-5D.
- Complete PGA.
- Allow the subject to complete the Patient Global Assessment of Disease (PtGA), BEFORE study drug administration.

- Perform endoscopy and collect biopsy specimens within 7 days of the Early Termination visit unless not indicated based on the subject's condition, at the PI's discretion.
- Schedule the Final Study Visit. The Final Study Visit is not required if the Early Termination visit occurs 6 or more weeks after the last study drug administration.

12 DEFINITION OF END OF STUDY

The end of study is defined as the last study visit (Visit 9; Week 16/Day 112, Final Study Visit) for the last subject randomized.

13 EFFICACY ASSESSMENTS

13.1 IMMUNOLOGICAL RESPONSE: ASSESSMENT OF ABERRANT INTRAEPITHELIAL LYMPHOCYTES

The primary endpoint in this trial is the reduction in the % of aberrant intestinal IELs with respect to total IELs as assessed by flow-cytometry (Immunological Response 1). The first secondary endpoint is Immunological Response 2, the reduction in the % of aberrant intestinal IELs with respect to intestinal epithelial cells, a composite endpoint calculated by multiplying the % of aberrant IEL vs total IELs (determined by flow cytometry) by the % of total IEL vs intestinal epithelial cells, as assessed by immunohistochemistry. The secondary endpoint could be more representative of a benefit driven by functional impact rather than simple reduction in IEL numbers.

Both endpoints address the core abnormality in RCD-II, an in situ small bowel T cell lymphoma in which aberrant lymphocytes are responsible for mucosal damage and symptoms and for the progression to EATL. Aberrant IELs are described as surface CD3-negative, intracellular CD3-positive. The reduction in the proportion and number of aberrant lymphocytes is specific to RCD-II, is analogous to a reduction in tumor size in a solid tumor cancer, and has been proposed as the most direct measurement of efficacy in RCD-II (as reviewed in van Wanrooij *et al.*, 2014).

This exploratory study, first industry-sponsored trial in RCD-II, will be considered positive for the purposes of Go-No decision-making if at least one of the two calculations of Immunological Response is found to be positive.

Flow cytometry is the most accurate tool available to quantify aberrant IELs (van Wanrooij *et al.*, 2014), and it is preferred over IHC, (less sensitive) and TcR rearrangement or clonality by polymerase chain reaction (PCR, less specific) (van Wanrooij *et al.*, 2014). Enumeration of total IELs will be done by IHC to calculate the secondary endpoint of % of aberrant IELs vs intestinal epithelial cells. Enumeration of aberrant (intracellular CD3) and abnormal (altered phenotype, such as overexpression of NKG2D) IELs by IHC and PCR will be performed as well, as exploratory endpoints.

Flow cytometry of IELs requires the acquisition of fragment(s) of small bowel tissue by endoscopy and biopsy, and the method to disperse, stain and analyze the IELs is described elsewhere (Leon, 2011).

Flow cytometry is the clinical-grade technique employed and validated in the routine phenotyping of hematological cancers such as leukemias and lymphomas. It is exquisitely quantitative (>10,000 single cells are quantified by laser beams per second based on multiple specific surface markers) (Leon 2011, van Wanrooij *et al*, 2014). The large number of cells stained and analyzed, estimated to be between 0.5 million and 5 million per time point per patient, ensures low variability and reproducibility. All sites will use the same procedure and experimental protocol, and technical validation will be performed prior to study start.

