1.3 ROLE OF IL-15 IN CELIAC DISEASE

Substantial evidence suggests a pathophysiological role for IL-15 in celiac disease and RCD-II (reviewed in Abadie and Jabri *et al.*, 2014):

- Innate immunity;

- IL-15 is an essential, non-redundant growth and activation factor for the IELs which destroy the intestinal mucosa;
- The expression of IL-15 in the intestinal epithelium is necessary for villous atrophy;
- In some patients, IL-15 drives progression towards lymphomagenesis and potentially fatal RCD-II (Malamut *et al*, 2010)
- Adaptive immunity:
 - IL-15 enhances the presentation of deamidated gluten peptides (DGP) by antigen-presenting cells (APCs);
 - IL-15 renders the activated CD4+ T cells resistant to inhibition by regulatory T cells;
 - IL-15 has been proven to be a key factor in the loss of tolerance to food antigens (DePaolo *et al*, 2011; Korneychuk, *et al*, 2014)

By activating the intraepithelial lymphocytes (IELs), IL-15 is believed to be the main mediator in the mucosal damage that ensues in response to gluten exposure in celiac disease (Korneychuk *et al*, 2014). The expression of IL-15 in the intestinal epithelium is necessary for villous atrophy in animal models of celiac disease and circumstantial evidence suggests this to be the case in humans, as well. In addition, IL-15 renders effector T cells resistant to inhibition by regulatory T cells (Tregs) (Abadie and Jabri, 2014), promoting loss of tolerance to food antigens (DePaolo *et al*, 2011, Korneychuk *et al*, 2014).

One of the studied mouse models of celiac disease is an IL-15-transgenic mouse, in which IL-15 overexpression by gut epithelial cells leads to celiac-like disease, including T and B cell-mediated pathology (Yokoyama *et al*, 2009 and 2011). IEL apoptosis has been observed in this animal model after treatment with anti-IL-15 (Malamut *et al* 2010) or anti-IL-15-receptor mAbs (Yokoyama *et al* 2009).

In RCD-II, the role of IL-15 appears even clearer, and IL-15 is believed to be the main driver of transformation and maintenance of the aberrant IELs (Meresse *et al*, 2012). IL-15 is up-regulated in the intestinal mucosa of patients with RCD-II and, more importantly, incubation of RCD-II patient duodenal biopsies with the anti-IL-15 monoclonal antibody, AMG 714, blocked anti-apoptotic signaling via JAK3 and STAT5, leading to apoptosis of the clonal aberrant IELs (Malamut *et al*, 2010, reviewed in Meresse *et al* 2012).

1.4 AMG 714

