1.5.1 Pharmacology

In nonclinical experiments conducted with the original hybridoma-derived antibody, AMG 714-HYB was found to recognize an epitope that is essential for the interaction between human IL-15 (hIL-15) and its receptor complex. AMG 714-HYB showed a dose-dependent inhibition of IL-15-induced proliferation of peripheral blood T cells, and cell lines expressing IL-15 receptors, as well as a dose-dependent inhibition of hIL-15-induced TNF- α production. Specificity for IL-15 was demonstrated by lack of inhibitory effects on human IL-2 (hIL-2)-mediated proliferation of peripheral blood T cells, on hIL-2-mediated TNF- α production, or on IL-2 induced cytotoxic T cell line (CTLL2) cell proliferation.

[REDACTED]

AMG 714-CHO was found to be efficacious in a mouse model of celiac disease triggered by the transgenic expression of human IL-15 in the gut epithelium (Malamut *et al*, 2010). In this model, AMG 714-CHO prevented IEL activation and proliferation, as well as histological abnormalities. In addition, AMG 714-CHO was able to induce apoptosis of human IELs in *ex vivo* culture of small intestinal explants from active celiac disease and RCD-II patients (Malamut *et al*, 2010). In this culture experiment, AMG 714-CHO resulted in a suppression of IL-15-driven anti-apoptotic signaling via JAK3 and STAT5.

In vitro studies demonstrated that AMG 714-CHO had high binding affinity for hIL-15, but lower affinity for macaque IL-15. Additionally, AMG 714-CHO neutralized hIL-15 but did not efficiently neutralize macaque IL-15. To enable preclinical studies in macaques, a surrogate antibody, Hu714MuXHu, was developed by fusing the F(ab) portion of a mouse anti-hIL-15 monoclonal antibody known to neutralize macaque IL-15, M111, with human IgG1 Fc. Hu714MuXHu was shown to neutralize macaque IL-15 with approximately the same potency as AMG 714-CHO neutralizes hIL-15.

In a safety pharmacology study, cardiovascular, respiratory, and neurobehavioral endpoints were evaluated in cynomolgus monkeys that received a single intravenous (IV) bolus dose of ≤ 300 mg/kg Hu714MuXHu. In this study, the no-observed-effect level (NOEL) was 300 mg/kg, the highest dose tested.

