13.2 HISTOLOGIC RESPONSE: SMALL BOWEL ENDOSCOPY, BIOPSY AND HISTOLOGY

At each time point specified in Table 1, small-bowel biopsies will be collected in order to perform the aberrant IEL analysis and the histological assessment of mucosal inflammation. The latter will provide the secondary endpoint of Histological Response, as measured by improvement from baseline in small intestinal VH:CD ratio assessed with a validated morphometric analysis (Taavela *et al*, 2013). Lack of Histological Response has been shown to correlate with long term outcomes including progression to EATL (Nijeboer *et al*, 2015 a, b), albeit the current Phase 2a study may be of insufficient duration to fully assess histological recovery (slower than immunologic resolution). In addition to the VH:CD ratio, the second commonly used histological score, the Marsh-Oberhuber classification (Marsh, 1992, Oberhuber 2000), as well as the total IEL count (all IEL, not just aberrant) will also be calculated as a secondary endpoint.

At each time point specified in Table 1, approximately eleven to thirteen (11-13) fragments or specimens of small-bowel tissue will be taken from the second part of the duodenum distal to the ampulla by trans-oral upper endoscopy and forceps biopsy. Biopsies should be collected from the D2 segment of the duodenum. Ulcerative lesions should be avoided. The location and macroscopic appearance of the tissue will be noted in the source documents. The potential presence of any observable lesion such as ulcerative jejunitis will be captured in the eCRF. When necessary, samples will be re-oriented and sectioned again until they are of good quality. The procedures will be described in a Study or Laboratory Manual or similar document, and the IEL/LPL preparation method will be based on published methods by the Paris site. The fragments or specimens will be prioritized as follows:

- i. First five specimens collected, for flow cytometry: Approximately 5 biopsy specimens will be used for flow cytometry, done locally at each site with fresh tissue.
- ii. Second three specimens collected, for histology and immunohistochemistry: Approximately three (3) biopsy specimens will be fixed in 10% formalin or other fixative, with one (1) of them used for standard pathology at the site and two (2) of them embedded in paraffin wax after orientation for analysis

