22.5 EFFICACY ANALYSES

22.5.1 PRIMARY ENDPOINT

The primary endpoint is the Immunological Response 1: reduction at Week 12 in % aberrant IELs vs total IEL as assessed by flow-cytometry between the AMG 714 and placebo arms.

The primary endpoint will be tested as follows:

$$H_0: \mu_{AMG\ 714} = \mu_{placebo}$$

against the alternative

$$H_1: \mu_{AMG\ 714} \neq \mu_{placebo}$$

where $\mu_{AMG\ 714}$ and $\mu_{placebo}$ denote the mean baseline to Week 12 reduction in % aberrant IELs vs total IELs as assessed by flow-cytometry in the AMG 714 and placebo arm respectively. The hypotheses will be tested using a two-sided type 1 error level of 10%.

The primary endpoint will be analyzed using analysis of covariance (ANCOVA) based on the per protocol population (PP), where baseline % aberrant IEL will be included as a covariate and treatment group as a fixed effect in the statistical model. The analysis will also include the percentage of patients with normalization of IEL counts by flow cytometry (aberrant IELs < 20% of total IEL).

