8.2 General statistical considerations

Descriptive statistics (e.g. mean, median, standard deviation (SD), minimum (MIN), maximum (MAX), and number of subjects with an observation (N) or missing observation (NMISS)) are used for summarizing continuous variables. Additional statistics will be provided for PK-related data, including the geometric mean, SD of log-transformed data, geometric CV% and geometric N (i.e. number of subjects with an observation that are included in the natural logarithmic transformation).

Frequencies and percentages are used for summarizing categorical variables.

All summary statistics will be presented by treatment arm and if repeated measures, then by visit/collection time point.

All listings will be created using ITT population. The PP and ITT flags for each subject will be included in all listings.

All tests will be two-sided, if not stated differently. P-values smaller than 0.1 (for primary hypothesis) or 0.05 (all other hypotheses) will be considered statistically significant. In addition to the inferential statistics, 90% or 95% confidence intervals will be constructed. For the primary endpoint a 90% confidence interval of the treatment difference will be

constructed. Ninety-five percent (95%) confidence intervals will be constructed for the individual treatment point estimates.

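### Should a Go on Immunological Response 2 alone require that the primary endpoint, Response 1, has not worsened?

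*Protocol*

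**What the plan says.** Protocol 13.1 names two immunological measures. Response 1, the primary endpoint, is aberrant IELs as a share of all IELs by flow cytometry. Response 2, the first secondary endpoint, is obtained "by multiplying the % of aberrant IEL vs total IELs (determined by flow cytometry) by the % of total IEL vs intestinal epithelial cells", the second factor coming from immunohistochemistry. SAP 8.6.2 gives the same product. The study is to be "considered positive for the purposes of Go-No decision-making if at least one of the two calculations of Immunological Response is found to be positive". The protocol offers Response 2 as possibly a better reflection of "a benefit driven by functional impact rather than simple reduction in IEL numbers". The same section says that both measures bear on the central disease process, and it treats a fall in either the share or the count of aberrant cells as efficacy, by analogy with a shrinking tumour.

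The Go rule in 13.1 states no significance level and no direction. SAP 8.2 supplies the levels: "P-values smaller than 0.1 (for primary hypothesis) or 0.05 (all other hypotheses) will be considered statistically significant". SAP sections 6 and 8.6.1 keep Response 1 as the only primary hypothesis. The SAP does not repeat the Go rule. On total IEL density, Protocol 13.2 says that "the total IEL count (all IEL, not just aberrant) will also be calculated as a secondary endpoint".

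**The concern.** The rule puts no condition on Response 1 when only Response 2 is positive. Total IEL density counts every IEL, so a drug that thins out IELs without favouring the aberrant ones would lower Response 2 and leave the fraction alone. The protocol makes such an effect believable. Section 1.3 states that "IL-15 is an essential, non-redundant growth and activation factor for the IELs which destroy the intestinal mucosa", and section 1.5.1 reports IEL apoptosis in ex vivo "culture of small intestinal explants from active celiac disease and RCD-II patients", while Table 2 lists no aberrant IELs in uncomplicated celiac disease.

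The stated rationale also sits badly with the formula. Of the two measures, Response 2 is the one that moves with plain IEL numbers.

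The diagnosis, the normalization threshold and the sample size all rest on the fraction. A development decision could therefore be called positive with the primary endpoint flat or moving the wrong way, and nothing in the rule would mark that case as different.

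**Working it through.** **The plan's own figure.** Inputs from Protocol 22.1: difference 20 points, SD 17.4, two-sided level 0.10, 16 and 8 subjects. Standard error = 17.4 × √(1/16 + 1/8) = 7.53; noncentrality = 20/7.53 = 2.65 on 22 df; power = 82.3%. The planned 80% is met, for Response 1 only.

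**Algebra of Response 2.** Let A be the aberrant fraction and D the total IEL density. The ratio of Response 2 after to before is (A1/A0) × (D1/D0). If A is unchanged, the relative change in Response 2 equals that in D. If D falls by a proportion d, Response 2 still falls unless A rises by more than d/(1 − d):

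| Density fall | Break-even relative rise in fraction |
|---|---|
| 20% | 0.20/0.80 = 25% |
| 30% | 0.30/0.70 = 43% |
| 40% | 0.40/0.60 = 67% |

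**False Go with no effect on either measure.** In the beneficial direction the levels are 0.05 (Response 1) and 0.025 (Response 2), so the bound is 0.05 + 0.025 = 7.5%. At correlations of 0.5, 0.8 and 0.9 between the two tests, the chance is 6.8%, 6.0% and 5.5%.

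**How often a general fall gives a Go.** The documents give neither the baseline values nor the variability of Response 2, so these are assumptions: mean fraction 45 or 60 (SD 20, clipped to 21-98), median density 60 with log-SD 0.4, and within-subject log-SDs (flow/IHC) of 0.35/0.15, 0.28/0.25 and 0.20/0.40. The first setting, at mean 60, gives an SD of change of 17.9 points, near the planned 17.4. The model is the SAP ANCOVA on relative change. With the fraction flat and density down 30%:

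- Go on Response 2 alone: 38-57% of trials.
- The same with the Response 1 estimate favouring placebo: 13-18% of trials.

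**What a sign condition would do.** Suppose a Go on Response 2 also required the Response 1 estimate not to favour placebo.

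1. Flat fraction, density −30%: Go on Response 2 alone remains in 23-40% of trials. With a truly flat fraction, the sign of Response 1 is close to a coin toss.
2. Fraction 10% worse, density −30%: it falls from 26-41% to 7-23%. At a 60% baseline this scenario means that aberrant cells fall by 1 − 1.1 × 0.7 = 23%, while normal IELs fall by 1 − (0.34 × 0.7)/0.40 = 40%. The drug would have to spare the aberrant cells.
3. The drug kills 40% of aberrant and 20% of normal IELs (assumed rates). At a 60% baseline the fraction becomes 0.36/(0.36 + 0.32) = 52.9%, a relative fall of 12%; at 80% it becomes 0.48/(0.48 + 0.16) = 75%, a relative fall of 6%. Response 2 falls by 40% in both cases. The chance of a Go across the three variance settings is:

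| Baseline mean | Current rule | With sign condition |
|---|---|---|
| 60% | 0.87 / 0.86 / 0.76 | 0.76 / 0.77 / 0.73 |
| 80% | 0.93 / 0.89 / 0.74 | 0.67 / 0.69 / 0.63 |

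4. Purely selective 40% kill, baseline mean 80%: from 0.92 / 0.88 / 0.79 to 0.80 / 0.80 / 0.76.

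**Why the fraction can miss a selective effect.** Take 100 IELs, 90 of them aberrant, and remove half of the aberrant cells and nothing else. The fraction goes from 90% to 45/55 = 81.8%, a relative fall of 9%. Aberrant cells per epithelial cell fall by 50% and total IELs by 45%.

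**The case for a change.** The strongest case for a change is that the defect is algebraic and needs no assumption, that the pharmacology in the protocol makes a general IEL fall plausible, and that the remedy is one sentence of SAP text. If the drug lowers the fraction by a third, the sign condition does indeed cost almost nothing: the chance of a Go is 0.81-0.997 with or without it, and if density also falls 30% the largest loss is from 0.990 to 0.987. The condition also works well when the fraction truly worsens.

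The algebra stands, and so does the awkwardness of the rationale sentence in 13.1. The claim of a nearly free remedy does not. It holds for a large effect on the fraction, but not where Response 2 adds most, namely when most IELs are aberrant and the fraction barely moves. In the flat-fraction case, which is the heart of the concern, the condition leaves most of the Response 2-only decisions in place. The worsening case, where it helps most, runs against Protocol 1.3, which holds IL-15 to be what sustains the aberrant cells and reports that AMG 714 drove those clonal cells into apoptosis in patient biopsies.

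A softer request would be to report a Go on Response 2 alone as one in which the primary endpoint was not met, with fraction and density shown beside it. SAP 8.6.1 and 8.6.2 already name Response 1 as primary and tabulate Response 1, Response 2 and total IEL density by arm, in relative and absolute terms. A reader can see at once which factor moved. SAP 8.7.5 describes Response 2 as an immunochemistry measure, which does not match the product in 8.6.2; that is a loose label in a list of variables to plot, and the formula in 8.6.2 governs.

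**Conclusion.** No change is needed. A large enough general fall in IELs can yield a Go with the primary endpoint flat, but the protocol accepts that outcome by design, because fewer aberrant cells per epithelial cell counts as benefit there. The rule serves an internal decision in an exploratory study of 24 subjects and does not touch the 0.10 test of Response 1. Its price under no effect is at most 2.5 percentage points of false Go in the beneficial direction (7.5% against 5%). Gating on the sign of Response 1 is a trade-off: it removes 13-18 points of Response 2-only Go when the fraction is flat and density falls 30%, and it gives up as much as 0.93 − 0.67 = 26 points of Go when the drug kills mainly aberrant cells in patients with high fractions. Leaving 13.1 silent on level and direction is a gap that SAP 8.2 and the word reduction in the endpoint definitions fill. The break-even figures and the 7.5% bound are exact; the simulated percentages rest on assumed baselines, variances and kill rates, and would shift with them.
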